Study title	A randomized, open-label, phase Ib clinical study comparing Fruquintinib 4mg qd continuous with 5 mg qd 3-week on/1-week off as 3 rd -line or above treatment in patients with advanced colorectal cancer who have failed with standard therapy
Sponsor	Hutchison Medi Pharma (Shanghai) Co., Ltd.
Principle of drug action	
Fruquintinib is a potent, anti-angiogenic small molecular compound with vascular endothelial growth factor (VEGF) receptor kinase family (VEGFR1, 2 and 3) as the target. Fruquintinib has a very high selectivity for kinase, with a good pharmacokinetic profile and safety index in animal models, and showed a powerful tumor inhibition in a variety of human tumor models in nude mice. At the same dose, its antitumor activity is more potent than sunitinib.
 
Phase I clinical trial on tolerability showed Fruquintinib had a significant antitumor activity for advanced intestinal cancer, gastric cancer, lung cancer and breast cancer.

Study Sites	Two study sites: Fudan University Shanghai Cancer Center, Sun Yat-sen University Cancer Center
Planned number of patients	
About 60 subjects are planned to be enrolled.
 
40 patients are enrolled in the randomized comparison part, and about 20 patients are added for the single-arm expansion part.
 
Randomized comparison part: Group A (4mg daily)-20 patients; group B (5 mg 3-week on/1-week off)-20 patients
 
Expansion part: 5mg qd 3-week on/1-week off – about 20 patients

Target Population	
Histologically or cytologically confirmed advanced colorectal cancer after failure of second-line and above chemotherapy or standard care.
 
Note: treatment failure is defined as: progression of disease
 
a. each-line of therapy for progressive disease includes one or multiple drugs used for ≥1 cycle or longer time
 
b. Early adjuvant/neoadjuvant therapy is allowed. If recurrence or metastasis occurs during or within 6 months after the completion of adjuvant/neoadjuvant therapy, the adjuvant/neoadjuvant therapy is considered as one first-line early systemic chemotherapy for one progressive disease.
 
c. The early therapy allowed is defined as chemotherapy combined with targeted drugs except VEGFR

Study start and end time	
The recruitment period for the randomized comparison part is estimated to be 8 months. The recruitment period for the expansion part is estimated to be 4 months.
 
Estimated start time: December 2012
 
Enrollment completion time for the expansion part: January 24, 2014
 
End time: October 24, 2014

Study objectives	
Primary objective:
 
To randomly compare the safety and tolerability of two different administration methods of Fruquintinib (4mg qd daily vs. 5mg qd 3-week on/1-week off) in treatment of patients with advanced colorectal cancer who have failed with standard care (evaluated according to CTCAE4.0), as to further determine the recommended dose for phase II/III clinical studies.
 
To further observe and evaluate the safety, tolerability and efficacy (progression-free survival) of Fruquintinib 5mg qd 3-week on/1-week off in treatment of patients with advanced colorectal cancer who have failed with standard care during the expansion

	part.
	
Secondary objective:
 
 To compare the objective response rate (ORR), disease control rate (DCR), duration of response (according to RECIST 1.1 criteria), progression-free survival (PFS) and overall survival (OS) between two groups To compare the pharmacokinetic profile of two different administration methods of Fruquintinib monotherapy in treatment of advanced colorectal cancer Expansion part- to further observe the DCR, ORR and OS of Fruquintinib in treatment of advanced colorectal cancer
Trial Design	
This is a randomized, multi-center, phase Ib clinical study comparing the safety and efficacy of two administration methods of Fruquintinib in treatment of patients with advanced colorectal cancer who have failed with standard care, as to further determine the administration method and recommended dose for phase II/III studies.
 
The study will be conducted in two parts:
 
 Randomized comparison part: to compare the safety and efficacy of two administration methods of Fruquintinib in treatment of patients with advanced colorectal cancer who have failed with standard care, as to further determine the recommended dose for phase II/III studies. Expansion part: to perform the expansion part with the determined recommended dose for phase II/III studies. The regimen of 5mg qd 3-week on/1-week off is selected for expansion part according to the results from randomized comparison part. 
All the patients will receive Fruquintinib monotherapy in a cycle of 4 weeks, and receive tumor assessment every 8 weeks until progression of disease, intolerable toxicity or withdrawal of informed consent.

Dosage and route of administration	
Randomized comparison part:
 
Group A: Fruquintinib 4mg qd po, daily
 
Group B: Fruquintinib 5mg qd po, 3-week on/1-week off
 
Expansion part: Fruquintinib 5mg qd po, 3-week on/1-week off

assessment	
Safety	
The adverse event is adjudicated and graded in accordance with NCI-CTCAE V4.0. The comprehensive evaluation of safety and tolerability is performed according to the severity and incidence of adverse event. The primary safety endpoints includes the overall incidence of adverse events, incidence of Grade 3/4 adverse events and serious adverse events.
 
The tolerability will be comprehensively evaluated based on the occurrence of discontinuation of the drug or dose reduction due to adverse event.

Effectiveness	
Randomized comparison part:
 
The secondary endpoints are objective response rate, disease control rate, duration of response, progression-free survival and overall survival determined in accordance with RECIST1.1
 
Expansion part:
 
The primary efficacy endpoint is progression-free survival at Week 16
 
The secondary efficacy endpoints are DCR, ORR and OS.

PK study	
To explore the pharmacokinetic (PK) profile of two different administration methods of Fruquintinib (4mg qd daily vs. 5mg qd 3-week on/1-week off), and to explore the relationship between PK and preliminary pharmacodynamic parameters as well as the main safety parameters

Inclusion Criteria	
All the following conditions must be met:
 
 Fully understanding of this study and voluntary signature of the informed consent form; Histologically and/or cytologically confirmed advanced colorectal cancer after

-
- 2nd-line or above treatment failure;
3. No systemic antitumor treatment or radiotherapy, immunotherapy, biological or hormone therapy in the past 4 weeks; no treatment with VEGFR inhibitor;
 4. Age = 18-70 years
 5. Body weight >40KG;
 6. Eastern cooperative oncology group (ECOG) score 0 or 1, and no exacerbation within 7 days;
 7. Evaluation of cardiac function: left ventricular ejection fraction $\geq 50\%$ (echocardiography);
 8. Definitely measurable lesion according to RECIST1.1;
 9. Expected survival > 12 weeks.
-

Patients meeting any of the following conditions must be excluded from this study:

1. Absolute neutrophil count (ANC) $< 1.5 \times 10^9/L$, platelet count $< 80 \times 10^9/L$ or hemoglobin $< 9g/dL$ in the laboratory test performed within one week prior to enrollment;
 2. Serum total bilirubin, glutamic-pyruvic transaminase, glutamic-oxaloacetic transaminase and alkaline phosphatase exceeding normal range (based on the normal value at clinical study site); alkaline phosphatase more than $2.5 \times ULN$ for patients with liver metastasis;
 3. Serum creatinine exceeding the upper limit of normal range (based on the normal value at clinical study site) or creatinine clearance lower than 50ml/min;
 4. Systolic blood pressure $\geq 150mmHg$ and/or diastolic blood pressure $\geq 100mmHg$ regardless of the use of antihypertensive agent;
 5. Serum potassium exceeding normal range with clinical significance, regardless of the supplementation of potassium preparation;
 6. Serum calcium or magnesium exceeding normal range with clinical significance, regardless of any supplementation;
 7. Urine protein 2+ or above, or 24-hour amount of urine protein $\geq 1.0g/24h$;
 8. Evidence of intestinal cavity infiltration of the tumor (with possibility of potential bleeding);
 9. Unrecovered toxicity from previous anticancer therapy (CTCAE > 1), not completely recovered from previous surgery or less than 4 weeks from the last anticancer therapy or surgery;
 10. Presence of metastasis to central nervous system (CNS);
 11. Clinically uncontrolled active infection, such as acute pneumonia, active phase of hepatitis B;
 12. Dysphagia or known malabsorption to drugs;
 13. Current digestive diseases such as duodenal ulcer, ulcerative colitis, or other conditions to possibly cause digestive tract bleeding or perforation as judged by investigators;
 14. Bleeding tendency or history of bleeding within 2 months prior to enrollment, regardless of the severity;
 15. Development of stroke within 12 months prior to enrollment, including transient ischemic attack;
 16. Activated partial thromboplastin time (APTT) or/and INR and prothrombin time (PT) exceeding normal range with clinical significance (based on the normal value at clinical study site);
 17. Incomplete healing of skin wound, severe mucosal ulcer or bone fracture;
 18. Acute myocardial infarction, severe/unstable angina pectoris or coronary bypass surgery within 6 months prior to enrollment; history of arterial thrombosis or serious deep venous thrombosis
 19. Pregnant or lactating women or positive pregnancy test in women of childbearing potential prior to the first dose; premenopausal female subjects who are unwilling to use appropriate contraceptive measures (over one year from the last
-

Exclusion Criteria

	menstruation) 20. Unsuitability to participating in the clinical study due to any clinical or laboratory abnormality as considered by investigators; 21. Severe mental or psychological illness, and inadequate compliance with the clinical study could be anticipated; 22. Participation in clinical trial of other drugs within the last 4 weeks.
Subjects Terminating Study	the Criteria on completion of the trial: 1. Progression of disease 2. Death 3. Inability to recover to \leq NCI CTC AE Grade 1 or baseline within 14 days after dose interruption 4. NCI CTC AE Grade 4 (nephrotic syndrome) in routine urinalysis or 24-hour urine protein quantification; CTC AE Grade 4 abnormal hepatic function and hemorrhage Criteria on premature discontinuation: 1. The subject becomes pregnant. 2. The investigator judges the termination of the study in the subject's best interest; 3. The subject or his/her legal representative requestes withdrawal from the study; 4. The subject is lost to follow-up 5. Serious violation from the study protocol
End of the whole trial	The whole trial ends 9 months after the end of enrollment for the expansion part.
Statistical analysis:	SAS 9.2 software is used for analysis, where the pharmacokinetic parameters are calculated using WinNonlin software. The detailed statistical method will be provided in the statistical analysis plan. In the randomized comparison part, statistical analysis and comprehensive evaluation will be performed for the primary parameters including safety and tolerability (overall incidence of adverse events, incidence of G3/4 adverse events, incidence of serious adverse events, incidence of adverse events leading to dose interruption and permanent discontinuation of the drug) and secondary parameters including the efficacy, as to determine the recommended dose for phase II/III trials. In the expansion part, the safety, tolerability and efficacy of Fruquintinib 5mg 3-week on/1-week off are further evaluated in patients with advanced colorectal cancer. The primary endpoints (safety, tolerability and progression-free survival at Week 16) are analyzed three months after the inclusion of the last subject in the expansion part. The overall survival is analyzed 9 months after the inclusion of the last subject in the expansion part.
Efficacy	To perform statistical description of objective response rate (proportion of subjects with complete response or partial response as the optimal overall response, according to RECIST1.1 criteria), DCR, DOR, PFS and OS.
Safety	All the adverse events will be listed by subject, and MedDRA is used to code adverse events by organ system and standard terminology for statistical description. Abnormal values in laboratory examinations, vital signs, ECG and other safety parameters are described by subject list. The overall incidence of adverse reactions, incidence of G3/4 adverse events and incidence of serious adverse events are compared and evaluated for the safety between the two groups. Proportions of dose interruption /dose reduction as well as permanent discontinuation due to study related adverse reaction are compared and evaluated for the tolerability between the two groups. Expansion part- the safety and tolerability of 5mg qd 3-week on/1-week off are further observed in treatment of advanced colorectal cancer. The overall incidence of adverse reactions, incidence of G3/4 adverse events and incidence of serious adverse events

	are evaluated.
Pharmacokinetic Studies	Non-compartment model analysis of data on the plasma concentration is performed by the central laboratory using WinNonlin software (enterprise edition). One-way analysis of variance will be used for the C _{max} , AUC _{0-∞} , and AUC _{0-t} (to be determined according to the opinions from the department of pharmacokinetics) during the trial, using dose group as the fixed factor.

(Emergency) contact of Hutchison Medi Pharma (Shanghai) Co., Ltd.....	3
Synopsis of phase Ib clinical study protocol	4
Abbreviations and Special Term	11
1. Background.....	14
1.1 Colorectal cancer.....	14
1.2 Fruquintinib.....	15
1.2.1 Preclinical evidence of Fruquintinib	15
1.2.2 Results of phase I clinical trial of Fruquintinib (preliminary results as of October 30, 2012)	16
1.2.2.1 Maximum tolerated dose (MTD) of Fruquintinib in subjects with advanced malignant solid tumor	16
1.2.2.2 Safety and tolerability.....	17
1.2.2.3 Observation of clinical efficacy:	25
1.2.2.4 Recommended dose for phase Ib clinical trial	26
1.2.2.5 Pharmacodynamics results.....	26
1.2.3 Results from long-term toxicology study of Fruquintinib.....	26
1.2.3.1 Long-term toxicity study in SD rats given Fruquintinib orally for 26 weeks followed by 4-week recovery period	26
1.2.3.2 Long-term toxicity study in Beagle dogs given Fruquintinib (drug product) orally for 39 weeks followed by 4-week recovery period	27
2 Study objectives	27
2.1 Primary objectives	27
2.2 Secondary objectives.....	27
3 Trial Design	28
3.1 SUMMARY OF EXPERIMENTAL DESIGN	28

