3.1 SUMMARY OF EXPERIMENTAL DESIGN

3.1.1 Rationale for Study Design

This is a bicentric, open-label, phase Ib clinical trial comparing the safety and efficacy of two different administration methods of Fruquintinib in patients with advanced colorectal cancer after failure of standard care, as to further determine the recommended dose and administration method for phase II/III clinical studies.

This trial is comprised of two parts: randomized comparison part and expansion part.

Randomized comparison part: patients will be randomized into Group A or B after meeting the screening criteria.

Group A: Fruquintinib 4mg qd po, daily, until progression of disease, unacceptable toxicity or voluntary withdrawal from the trial in advance.

Group B: Fruquintinib 5mg/ qd po, 3-week on/1-week off, until progression of disease, unacceptable toxicity or voluntary withdrawal from the trial in advance.

28 days is one cycle of Fruquintinib treatment. Information on the subsequent antitumor therapy will be collected for the patient after progression of disease, unacceptable toxicity or voluntary withdrawal from the trial, and the patient's survival status will be followed up until death.

Expansion part: the recommended dose for phase II/III studies is determined for the expansion part based on the randomized comparison part.

3.1.2 Rationale for Dose Selection.

(1) Safety dose:

Phase I clinical tolerability study of Fruquintinib: A single dose within the range of no more than 6.0mg could be tolerated, and higher doses were not explored. Multi-doses of Fruquintinib once daily were given for consecutive 28 days in the phase I tolerability clinical trial, the main dose limiting toxicity (DLT) was hand-foot syndrome. Grade 3 hand-foot syndrome limited the subjects to receive 6.0mg dose and **the maximum tolerated dose was 4.0mg.**

Expansion part of administration for 3-week on/1-week off: 5.0mg and 6.0mg could be

tolerated, and higher doses were not explored. Only one DLT of asthenia occurred in 6.0mg dose group.

(2) Efficacy during the whole phase I tolerability trial:

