The main adverse reactions occurred during the trial included hand-foot syndrome, hoarseness, proteinuria, hypertension, stomatitis and asthenia. Grade 3 and above adverse events occurred in more than 10% subjects were hypertension (22.5%) and hand-foot syndrome (17.5%). 17 subjects in QD consecutive administration group (n=20) had grade 3 or above adverse events, 6 had grade 3 hand-foot syndrome, 6 had SAE and 7 discontinued the drug permanently for toxicity. 8 subjects in administration for 3-week on/1-week off (3/1) group (n=20) had grade 3 or above adverse events, 1 had grade 3 hand-foot syndrome, 4 had SAE and 4 discontinued the drug permanently for toxicity.

Efficacy in both the two groups: the DCR was 76.4%, there were 2 patients with PR+MR and mPFS had not reached 3.7m in QD group (17 evaluable patients); the DCR was 83.3%, there were 3 patients with PR+MR and the mPFS had reached 3.7m in 3/1 group (18

evaluable patients).

Preliminary conclusion: the administration method of 5mg 3/1 was not inferior to that of 4mg QD in terms of efficacy (in particular DCR and PFS), whilst it had a certain advantage over 4mg QD in terms of the occurrence of grade 3 or above adverse events, occurrence of grade 3 hand-foot syndrome, occurrence of SAEs and occurrence of AEs leading to permanent discontinuation of the drug. Therefore, the administration method of 5mg 3/1 was selected for the expansion part of phase Ib trial.

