5.1 Dosage and administration regimen of study drug

Randomized comparison part:

All the subjects will be randomized (1: 1) into Fruquintinib group A (4mg qd daily) and group B (5 mg qd 3-week on/1-week off).

Both of the groups will receive the treatment in a cycle of 4 weeks, until progression of disease, unacceptable toxicity or withdrawal of the informed consent.

Expansion part:

According to the preliminary results of the randomized comparison part, the administration method and recommended dose for phase II/III studies are determined as group B (5 mg qd 3-week on/1-week off) for the expansion part, using 4 weeks as one therapeutic cycle as well, until progression of disease, unacceptable toxicity or withdrawal of informed consent.

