6.2.1.2 Assessment of effectiveness

The tumor is evaluated in accordance with RECIST1.1 criteria, and the detailed evaluation criteria are provided in Appendix 2. The radiological evaluation of tumors could use CT or MRI as decided by investigators, however, the apparatus and technical parameters should keep consistent throughout the study; contrast agent should be used in case of no contraindications. If the tumor evaluation has been performed 14-21 days before the first dose, and the same method and apparatus are used in the same hospital, this evaluation could be used as the baseline tumor evaluation. The baseline tumor evaluation should include neck, chest, abdomen, pelvis and any other sites that are suspected to have tumor lesions. Bone scan should be used for follow-up of the disease in patients with bone metastasis.

Record of target lesions: number, site and description of lesions, the maximum diameter measured for each lesion (except lymph node) and the minimum diameter measured for lymph node, sum of diameters including all the target lesions;

Subjects will receive the first tumor evaluation after 2 cycles of treatment, and one evaluation every two cycles subsequently, until progression of disease. If complete response or partial response occurs, it needs to be confirmed after 4 weeks. If the patient interrupts the dose for adverse drug reaction or other reasons, the tumor evaluation will be performed once every 8 weeks as originally scheduled. If the patient discontinues the study drug within 56 days, the tumor evaluation should be performed as early as possible after discontinuation of the drug.

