6.2.5 Subsequent antitumor therapy

Information on subsequent antitumor therapy needs to be collected and recorded on the eCRF/CRF for patients with progression of disease, including name, dose of the drug and duration of administration. Any information on the radiotherapy for progression of disease will also be collected, including the site of radiotherapy, Gy dose, start and end time.

7 Safety evaluation

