8.1 Primary and secondary research variables

Primary variables:

Overall incidence of adverse events

Incidence of Grade 3/4 adverse events

Incidence of serious adverse events

Incidence of adverse events leading to permanent discontinuation

Incidence of adverse events leading to interruption/reduced dose

16-week progression-free survival rate

Secondary variable:

Effectiveness:

"Event occurrence date" variable: Calculated since the day when the informed consent is signed. If no event is observed, there is no date of end, and a so called cutoff observation has to be considered for analysis. The cutoff date is: The last date, such as for "last tumor measurement", "last medication registration", or "last visit".

Secondary efficacy variables include objective response rate, disease control rate, duration of response, progression-free survival, and overall survival.

Objective response rate (ORR): defined as the incidence of confirmed complete response (CR) or partial response (PR), the target lesions and non-target lesions are evaluated with validated radiological method and judged in accordance with RECIST criteria 1.1.

Progression-free survival (PFS): defined as the time from the signature of informed consent form to the first recording of progression of disease (PD) or date of death, whichever comes first. If no PD is observed, the censoring date should be the date of the last tumor measurement.

Overall survival (OS): defined as the time from the signature of informed consent form to date of death for any reason. If no death is observed, the last follow-up date is regarded as the censoring date.

Disease control rate (DCR): defined as the incidence of confirmed complete response (CR), partial response (PR) and stable disease (SD), the target lesions and non-target lesions are

evaluated with validated radiological method and judged in accordance with RECIST criteria 1.1.

Duration of response: defined as the time from the first recording of CR or PR to the first finding of PD for patients who have achieved response. For those with no record of PD after CR or PR, the censoring date is the date of the last tumor measurement.

Safety and Tolerability:

Safety and tolerability of the treatment are evaluated by incidence and severity of adverse events, laboratory tests, vital signs, ECG, LVEF, and ECOG performance status.

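### The synopsis stops tumor scans at intolerable toxicity while Section 6.2.1.2 and flowchart note 1 continue them to progression, so Week-16 PFS status can be lost after a toxicity stop

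*Protocol*

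**What the plan says.** **Synopsis, Trial Design.** One sentence covers both treatment and scanning. Under it patients "receive tumor assessment every 8 weeks until progression of disease, intolerable toxicity or withdrawal of informed consent".

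**Section 6.2.1.2.** "Subjects will receive the first tumor evaluation after 2 cycles of treatment, and one evaluation every two cycles subsequently, until progression of disease". Toxicity is not a reason to stop scanning. The section keeps the 8-week calendar during a dose interruption and asks for a scan as soon as possible if drug is stopped within 56 days. It does not name permanent discontinuation after that.

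**Study flowchart (Section 6).** In the copy at hand, the tumor-assessment row is marked at screening, Day 56 and Cycle 3+, and the later columns are blank. Note 1, attached to that row, continues scans to progression. For patients on drug for less than 56 days it makes the scan optional, at the investigator's judgement.

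**Section 8.1.** PFS ends at first recorded progression or death. Otherwise, "If no PD is observed, the censoring date should be the date of the last tumor measurement".

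**Endpoint.** Week-16 PFS is the primary efficacy endpoint of the expansion part (synopsis; Section 6.2.1.1). In the randomized part PFS is secondary.

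**Subsequent therapy.** Section 3.1.1: "Information on the subsequent antitumor therapy will be collected for the patient after progression of disease, unacceptable toxicity or voluntary withdrawal from the trial". Section 6.2.5: "Information on subsequent antitumor therapy needs to be collected and recorded on the eCRF/CRF for patients with progression of disease", with no mention of toxicity stops.

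**The concern.** The two stop rules for scanning cannot both be followed in a patient who leaves drug for toxicity without progression. The clearest case is a patient with a clean Week-8 scan who stops permanently at, say, Week 10. Section 6.2.1.2 and note 1 imply a Week-16 scan, and the synopsis says scanning has ended.

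Where the synopsis is followed, Section 8.1 allows two outcomes. A patient not known to have died is censored at the Week-8 scan. A patient who dies has an event dated at death, and if that falls after Week 16 the patient counts as progression-free at Week 16 although nobody looked after Week 8.

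This is a matter of data collection, so a later censoring rule cannot repair it: a scan that was not taken cannot be recovered. The protocol's own RECIST appendix (Appendix 2, Section 4.5) says that time-to-event endpoints need regular repeated assessment on a schedule unaffected by treatment delays or similar events.

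**Working it through.** The protocol gives no event, power or precision calculation for PFS, so there is no figure to reproduce. The check compares the passages and then sizes the consequence.

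**1. Rules for a permanent toxicity stop after Day 56**

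| Place | Does scanning continue? |
|---|---|
| Synopsis, Trial Design | No |
| Section 6.2.1.2, general rule | Yes, to progression |
| Section 6.2.1.2, off-drug sentences | Not covered |
| Flowchart grid | No mark after Cycle 3+ |
| Flowchart note 1 | Yes, to progression |

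**2. How many patients.** Section 3.1.2(3) reports for the 3-week on/1-week off group (n = 20) that "4 had SAE and 4 discontinued the drug permanently for toxicity", and 7 permanent toxicity stops among 20 on daily dosing. The proportions are 4/20 = 20% and 7/20 = 35%. These count all toxicity stops. The number falling between the Week-8 and Week-16 scans is not given.

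**3. Upper bound for the expansion part.** Assume 20% of 20 patients stop, all between the two scans: 0.20 × 20 = 4 patients without Week-16 status. The best-to-worst range is 4/20 = 20 points.

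Worked example (assumed counts): 4 progress at Week 8, 4 stop after a clean Week-8 scan, and 4 of the remaining 12 progress at Week 16.
- Kaplan-Meier: (1 − 4/20) × (1 − 4/12) = 0.80 × 0.667 = 53%.
- All four stoppers had progressed: 8/20 = 40%.
- None had progressed: 12/20 = 60%.

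**4. Expected bias (illustrative simulation).** Assumptions that are not in the protocol: exponential PFS; scans at Weeks 8 and 16; toxicity stops uniform over Weeks 2 to 14; progression hazard after stopping multiplied by 1 to 3; later deaths not counted. The median of 3.7 months is the interim value for the 3-week on/1-week off group (Section 3.1.2(3)).

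| Stopping | Hazard multiple | Week-16 PFS, scans to progression | Week-16 PFS, scans end at toxicity | Overstatement |
|---|---|---|---|---|
| 20% | 1 | 50.3% | 50.3% | 0 |
| 20% | 2 | 47.5% | 50.2% | 2.7 points |
| 20% | 3 | 45.4% | 50.2% | 4.8 points |
| 35% | 1 | 50.2% | 50.1% | about 0 |
| 35% | 2 | 45.2% | 50.1% | 4.9 points |
| 35% | 3 | 41.8% | 50.2% | 8.4 points |

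About 17% (at 20% stopping) and 30% (at 35%) of patients are censored before Week 16. The model also leaves patients who stop before Week 8 unscanned, although Section 6.2.1.2 asks for a scan then, and it ignores deaths. Both simplifications tend to enlarge the effect.

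**5. Arm difference.** 7/20 against 4/20 is a difference of 15 points, Newcombe 95% interval −12 to +40, Fisher exact p = 0.48. Power to detect 35% against 20% with 20 per group is about 18%.

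**The case against.** The strongest reply is that the synopsis sentence is a loosely worded treatment rule. Section 5.1 applies nearly the same list to treatment alone ("until progression of disease, unacceptable toxicity or withdrawal of the informed consent"), and so does Section 3.1.1. Both detailed scan rules, Section 6.2.1.2 and note 1, run to progression. That is probably the intent, but the synopsis as written says otherwise, the flowchart grid shows no later scan, and Section 6.2.1.2 is silent on permanent stops after Day 56. The reply supports correcting the wording and does not remove the conflict.

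Several stronger readings are tempting, and the protocol does not support them:

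- *The flowchart sides with the synopsis.* It does not. Its grid is blank after Cycle 3+, but note 1 to the same row agrees with Section 6.2.1.2.
- *Section 4.4 ends the trial for a toxicity stopper.* Its completion criteria stand under a treatment-termination heading. Section 4.6 lists when a subject's trial ends, and toxicity is not among the reasons. Section 4.6 does not, however, order scans for these patients.
- *Toxicity stoppers have no observed PFS outcome.* This holds only where a site follows the synopsis. Even then survival is followed and death is an event.
- *The loss is unequal between arms.* The counts include all stops whatever their timing, and the contrast is weak. The primary-endpoint issue also lies in a single-arm part.
- *Progression risk rises once drug is withdrawn.* The protocol gives no data on this for these patients. With an unchanged hazard the simulated bias is zero.

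It is also fair to say that sampling error is larger than the bias: with 20 patients, an exact 95% interval around 50% runs from about 27% to 73%.

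**Conclusion.** The contradiction stands and bears on how the expansion part's primary efficacy endpoint is ascertained. It should be settled in the protocol, because the loss cannot be made good at analysis.

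The bound of about 4 patients in 20 rests on Group B's interim stopping rate carrying over and on every stop falling between the Week-8 and Week-16 scans. Fewer patients are affected if stops come earlier or later, or if death by Week 16 settles the status. The figure of 0 to about 5 points rests on an assumed hazard after stopping. The direction, if there is a bias, is to overstate Week-16 PFS.

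Confidence is high that the passages conflict and moderate on the practical effect, which depends on the rule each of the two sites applies. No conclusion about the comparison of regimens follows.

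**What to change.** Write one assessment rule and repeat it in the synopsis, the flowchart grid, note 1 and Section 6.2.1.2, separately from the rule for stopping treatment. Suggested content: tumor assessment continues on the existing 8-week schedule until progression, death, withdrawal of consent to follow-up or end of trial, whatever the reason for stopping drug.

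- **Synopsis:** split the sentence so that the toxicity condition applies to treatment only.
- **Section 6.2.1.2:** name permanent discontinuation without progression alongside dose interruption.
- **Flowchart:** mark tumor assessment in the follow-up column for patients off drug without progression.
- **Stops within 56 days:** reconcile note 1, which makes the scan optional, with Section 6.2.1.2, which asks for it.
- **Separate minor item:** align Section 6.2.5 with Section 3.1.1 so that subsequent therapy is recorded after toxicity stops too. This does not enter PFS as Section 8.1 defines it.

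The cost is a short amendment and a few extra scans in patients who stop for toxicity without progression, scans that Section 6.2.1.2 already calls for. Treatment rules are unchanged.
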